### 10.3 Method of Unblinding

#### 10.3.1 Medical Emergency

No open key to the random code will be available to the study centers and Sponsor. Sealed code break envelopes will be held by the clinical site, medical monitor and/or Sponsor. In an emergency, the Investigator or other study team member may need to break the treatment code immediately, or

**CONFIDENTIAL**

as quickly as possible if this is in the best interest of the trial subject. The breaking of the blind should only occur where knowledge of the study medication treatment will affect the subject's clinical management. The Medical Monitor should be consulted prior to the breaking of the blind.

If the code is broken the envelope must be signed and dated by the individual who broke the code, and information entered into the subject's source documents, explaining the reason and date that it was opened, identity of the person who authorized the code break, and documenting the identity of the study product allocated to the subject. This must be countersigned by the Investigator.

### 10.3.2 End of Study

The randomization code will be broken by the blinded Study Statistician once data entry has been completed, the database locked, and the per-protocol population for analysis established. Sponsor will provide written permission to the Study Statistician prior to the breaking of the randomization code.

## 10.4 Investigational Products

### 10.4.1 Supply

Moxidectin will be supplied by the Sponsor as 100 mg uncoated, oval-shaped tablets containing the components listed in [Table 9](#). Moxidectin tablets contain 2 mg moxidectin.

**Table 9 Moxidectin Tablet Components**

| Component                  | Quality Reference          | Function          |
|----------------------------|----------------------------|-------------------|
| Micronized moxidectin      | United States Pharmacopeia | Active ingredient |
| Microcrystalline cellulose | National Formulary         | Diluent           |
| Lactose, anhydrous         | National Formulary         | Diluent           |
| Sodium lauryl sulfate      | National Formulary         | Surfactant        |
| Colloidal silicon dioxide  | National Formulary         | Glidant           |
| Croscarmellose sodium      | National Formulary         | Disintegrant      |
| Magnesium stearate         | National Formulary         | Lubricant         |
| Nitrogen                   | National Formulary         | Processing aid    |

Placebo tablets will be matched in appearance to the active study drug and will contain the same excipients but will not contain moxidectin.

### 10.4.2 Packaging and Labelling

Moxidectin will be supplied to the site packaged in high density polyethylene bottles. Moxidectin will be shipped to site after receipt of required documentation of study approval and in accordance with applicable regulatory requirements.

Product labelling will be in accordance with local regulations and requirements and will include at a minimum:

- Sponsor name
- Protocol number
- Product name or drug code
- Dose or product strength
- Route of administration
- Lot number
- Directions for use
- Expiry date or retest date (on outer packaging)
- 'For Clinical Trial Use Only'

- Subject Number

Any specific cautionary statements will be included according to local law.

### 10.4.3 Storage and Handling

Moxidectin tablets and placebo to match must be stored at controlled room temperature (25°C) and protected from light and moisture. Tablets must not be frozen. Temperature excursions are permitted up to 30°C for up to 12 months.

Only participants enrolled in the study may receive investigational products. Prior to dispensing, moxidectin supplies will be stored securely under the appropriate conditions at the clinical trial site in a secure area with access limited to authorized staff, and according to relevant regulations.

The Investigator or authorized designee will ensure that the IMP is safely and securely stored in compliance with Good Laboratory Practice storage requirements. The Investigator is responsible for ensuring that the IMP is dispensed in accordance with the protocol and only to participants enrolled in the study. Authorized study personnel will dispense moxidectin.

### 10.4.4 Dosage and Administration of Test Drugs

Subjects may receive a maximum of 18 tablets for oral administration comprised of moxidectin 2 mg tablets and matched placebo to maintain the blind and accommodate the 36 mg dose. Administration will be observed by clinic staff to ensure compliance.

This pill burden is considered reasonable for this phase of study. Each moxidectin 2 mg and placebo to match tablet is 100 mg total weight and < 1 cm in length. Eighteen (18) tablets were administered without issue in MDGH-MOX-1008, where 60 healthy volunteers received 18 moxidectin 2 mg and/or matched placebo tablets per oral of the current formulation. No acceptability or compliance issues were reported in this study and all subjects were able to (and observed to) swallow the 18 tablets.

The dose of moxidectin will be administered on Day 0 after fasting from at least midnight and preferably overnight. Subjects will be required to swallow moxidectin with water. Subjects must continue to fast for 2 hours post-dose. Clear liquids may be consumed *ad libitum*.

### 10.4.5 Dispensing and Accountability

All IMP supplied is only for use in this clinical study and should not be used for any other purpose.

The Investigator or designee is responsible for maintaining accurate records for all study medications dispensed and returned. The inventory and dispensing logs must be available for inspection by the study monitor. Study product supplies, including partially used or empty bottles must be accounted for by the Investigator or designee and verified by the study monitor and returned to the drug repository for destruction at the end of the study.

When requested in writing by the Sponsor, unused study medication supplies may be destroyed by the Investigator provided such disposition can be performed safely. Records shall be maintained by the Investigator or any such alternate disposition of the study medication. These records must show the identification and quantity of each unit disposed of, the method of destruction (taking into account the requirements of local law), and the person who disposed of the test substance. Such records shall be submitted to the Sponsor.

## 11 CONCURRENT MEDICATIONS AND TREATMENTS

At each study visit or contact, the Investigator should question the subject about any medication taken. Concomitant therapies should be brought to the attention of the Investigator. Any such medications will be recorded on the CRF. Any changes in doses or introduction of new medications during the course of the study will also be recorded.

If the medication is related to the occurrence of an AE, ensure that details are recorded in the CRF.

### 11.1 Special Dietary Requirements

There are no special dietary requirements.

### 11.2 Concurrent Medications and Treatments

#### 11.2.1 Prior to Study Entry

Refer to Exclusion Criteria in [Section 8.3](#).

#### 11.2.2 During the Study Dosing Period

Every effort should be made to keep concurrent medications for chronic or ongoing medical issues stable throughout the study period.

All concurrent medications, including vitamin supplements and herbal remedies, must be recorded in the appropriate section of the CRF. All changes in medication will be noted. If the reason for use meets the definition of an AE, the AE will be recorded in the source documents for that subject and on the appropriate page of the CRF.

Except as specified in [Section 11.2.3](#), subjects may not receive treatment with any scabicide, including ivermectin, permethrin, benzyl benzoate, lindane, crotamiton, malathion or tea tree oil at any time up to and including Week 12.

Scabies symptoms including pruritus may persist for several weeks after successful treatment of the infestation. Subjects should not receive supportive therapies to manage their scabies symptoms or treatment with other anti-parasitic treatments (in addition to those listed above) up to and including Day 28. Should the subject report scabies symptoms that are intolerable, oral antihistamines may be used at the discretion of the Investigator.

Topical steroids and topical preparations containing zinc, calamine, tar or salicylic acid (including medicated emollients) are prohibited after Screening up to and including Day 28.

Unmedicated emollient creams are permitted at any time.

#### 11.2.3 Rescue Therapy

If subjects are shown to be either newly or persistently infected with confirmed scabies mites by RCM on or at any time from Day 14, standard of care may be offered. Rescue therapy may not be offered in the absence of scabies mites or based on symptomology only.

## 12 ADVERSE EVENTS AND TOXICITY MANAGEMENT

### 12.1 Safety Parameters

Safety assessments will include physical examination, AEs, vital signs and clinical laboratory tests.

### 12.2 Adverse Events

An AE is any untoward medical occurrence in a subject or clinical investigation subject administered an Investigational Product (whether it is the experimental product or control) and which does not necessarily have a causal relationship with the Investigational Product. An AE can therefore be any unfavorable and unintended sign, symptom, or disease temporally associated with the use of a medicinal product, whether or not considered related to the medicinal product. Pre-existing events that increase in frequency or severity or change in nature during or as a consequence of use of a drug in human clinical trials will also be considered as an AE. AEs may also include pre- or post-treatment complications that occur as a result of protocol-mandated procedures (e.g. invasive procedures such as biopsies).

Any AE (i.e. a new event or an exacerbation of a pre-existing condition) with an onset date after informed consent up to the last day on study (including the follow-up, off study medication period of the study), should be recorded as an AE on the appropriate CRF page(s).

An AE **does not** include:

- medical or surgical procedures (e.g. surgery, endoscopy, tooth extraction, transfusion); the condition that leads to the procedure is an AE;
- pre-existing diseases or conditions present or detected prior to start of study product administration, that do not worsen;
- situations where an untoward medical occurrence has not occurred (e.g. hospitalization for elective surgery, social and/or convenience admissions);
- overdose of either study product or concomitant medication without any signs or symptoms unless the subject is hospitalized for observation.

#### 12.2.1 Assessment of Adverse Events

All AEs will be assessed by the Investigator and recorded on the appropriate CRF page, including the date of onset and resolution, severity, relationship to study product, outcome and action taken with study medication. Each AE will be graded for severity using the FDA Guidance for Industry: Toxicity Grading Scale for Healthy Adult and Adolescent volunteers Enrolled in Preventive Vaccine Clinical Trials in [Appendix 18.1](#). For the purpose of monitoring toxicities, the Baseline value is defined as the last value prior to the administration of IMP.

For AEs not specifically identified in the grading table, the grades presented in [Table 10](#) should be applied

**Table 10 Grading of Adverse Events**

| Grade | Severity | Comments  |
|-------|----------|---|
| 1     | Mild     | Mild symptoms causing no or minimal interference with usual social & functional activities with intervention not indicated        |
| 2     | Moderate | Moderate symptoms causing greater than minimal interference with usual social & functional activities with intervention indicated |
| 3     | Severe   | Severe symptoms causing inability to perform usual social & functional activities with intervention or hospitalization indicated  |

| Grade | Severity         | Comments  |
|-------|------------------|---|
| 4     | Life-threatening | Potentially life-threatening symptoms causing inability to perform basic self-care functions with intervention indicated to prevent permanent impairment, persistent disability, or death |

The relationship to IMP therapy should be assessed using the definitions presented in [Table 11](#).

**Table 11 Assessment of Relationship of Adverse Events to Investigational Medicinal Product**

| Causality | Comment   |
|-----------|---|
| Unrelated | AE is clearly due to extraneous causes (e.g. underlying disease, environment, known effect of another drug)   |
| Unlikely  | The temporal association between the AE and study drug is such that study drug is not likely to have any reasonable association with the AE   |
| Possible  | The AE could have been produced by the subject's clinical state or study drug   |
| Probable  | The AE follows a reasonable temporal sequence from the time of study drug administration, abates upon discontinuation of the study drug and cannot be reasonably explained by the known characteristics of the subject's clinical state |
| Definite  | The AE follows a reasonable temporal sequence from the time of study drug administration, abates upon discontinuation of the study drug and/or reappears when study drug is re-introduced   |

These criteria in addition to good clinical judgment should be used as a guide for determining the causal assessment. If it is felt that the event is not related to study product, then an alternative explanation should be provided.

### 12.2.2 Adverse Event Reporting Period

All AEs, regardless of severity, causality or seriousness must be reported from the date of informed consent until the end of the study or 28 days after the last dose of study medication, whichever is later. However, any AE that the Investigator believes is at least possibly related to study medication should be reported regardless of time elapsed from the final dose.

## 12.3 Serious Adverse Events

### 12.3.1 Serious Adverse Event Definition

A **serious adverse event (SAE)** is defined as follows:

Any adverse drug experience occurring at any dose that results in any of the following outcomes:

- death;
- life-threatening situation (subject is at immediate risk of death);
- inpatient hospitalization or prolongation of existing hospitalization (excluding those for study therapy or placement of an indwelling catheter, unless associated with other serious events);
- persistent or significant disability/incapacity;
- congenital anomaly/birth defect in the offspring of a subject who received study product;

Important medical events that may not result in death, be immediately life-threatening, or require hospitalization, may be considered a SAE when, based upon appropriate medical judgment, they may jeopardize the subject and may require medical or surgical intervention to prevent one of the outcomes listed in this definition. Examples of such events are:

- blood dyscrasias or convulsions that do not result in hospitalization;
- development of drug dependency or drug abuse.

### 12.3.2 Clarification of Serious Adverse Events

- Death is an outcome of an AE, and not an AE in itself. In reports of death due to “Disease Progression”, where no other information is provided, the death will be assumed to have resulted from progression of the disease being treated with the study product(s).
- All deaths, regardless of cause, must be reported to the Sponsor for subjects on study and for deaths occurring within 30 days of last study product dose or within 30 days of last study evaluation, whichever is longer.
- “Occurring at any dose” does not imply that the subject is receiving study product at the time of the event. Dosing may have been given as treatment cycles or interrupted temporarily prior to the onset of the SAE, but may have contributed to the event.
- “Life-threatening” means that the subject was at immediate risk of death from the event as it occurred. This does not include an event that might have led to death, if it had occurred with greater severity.
- Complications that occur during hospitalizations are AEs. If a complication prolongs hospitalization, it is a SAE.
- “In-patient hospitalization” means the subject has been formally admitted to a hospital for medical reasons, for any length of time. This may or may not be overnight. It does not include presentation and care within an emergency department.
- The Investigator should attempt to establish a diagnosis of the event based on signs, symptoms and/or other clinical information. In such cases, the diagnosis should be documented as the AE and/or SAE and not the individual signs/symptoms.

### 12.3.3 Serious Adverse Event Reporting Requirements

#### 12.3.3.1 All Serious Adverse Events

The Sponsor has requirements for expedited reporting of SAEs meeting specific requirements to worldwide regulatory authorities; therefore, all appropriate parties must be notified immediately regarding the occurrence of any SAE that occurs during the study. The procedures for reporting all SAEs, regardless of whether the Investigator believes that the experience is related to study drug, are as follows:

- 1) Complete the “Serious Adverse Event Report Form”
- 2) Send the completed “Serious Adverse Event Report Form” to the Sponsor Safety Desk [REDACTED] within 24 hours of the Investigator’s knowledge of the event.
- 3) For fatal or life-threatening events, also submit copies of hospital case reports, autopsy reports, and other documents when requested and applicable

Additional detail on reporting SAEs is included in the SRM.

The Sponsor may request additional information from the Investigator to ensure the timely completion of accurate safety reports.

The Investigator must take all therapeutic measures necessary for resolution of the SAE. Any medications necessary for treatment of the SAE must be recorded onto the concurrent medication section of the subject’s CRF.

#### 12.3.3.2 Investigator Reporting Requirements for Serious Adverse Events

An SAE may qualify for reporting to regulatory authorities if the SAE is considered to have a possible causal relationship to the study product and is unexpected (Suspected Unexpected Serious

**CONFIDENTIAL**

Adverse Reaction [SUSAR]) based upon the current Investigator's Brochure. In this case for multi-center studies, all Investigators will receive a formal notification describing the SAE.

Where this is required by local regulatory authorities, and in accordance with the local institutional policy, the Investigator should notify (in writing) the local Independent Ethics Committee (IEC) of SAEs as soon as is practical.

## **12.4 Follow up of Serious and Non-Serious Adverse Events**

Follow-up of serious and non-serious AEs will continue through the last day on study (including the follow-up, off study medication period of the study), until the Investigator determines that the subject's condition is stable, or up to 30 days after the last dose of Study Product, whichever is longer. The Sponsor may request that certain AEs be followed until resolution.

## **12.5 Additional Considerations for Reporting Adverse Events**

### **12.5.1 Diagnosis Versus Signs and Symptoms**

Each AE will be recorded to represent a single diagnosis. Accompanying signs (including abnormal laboratory values or ECG findings) or symptoms will NOT be recorded as additional AEs. If a diagnosis is unknown, sign(s) or symptom(s) will be recorded as an AE(s).

### **12.5.2 Pre-existing Conditions**

Pre-existing conditions (present before the start of the AE collection period) are considered concurrent medical conditions and will NOT be recorded as AEs. However, if the subject experiences a worsening (severity or frequency) or complication of such a concurrent condition, the worsening or complication will be recorded as an AE. The Investigator will ensure that the AE term recorded captures the change in the condition (e.g., "worsening of...").

### **12.5.3 Elective or Pre-Planned Surgeries or Procedures:**

Procedures (surgeries or therapies) that were planned before the start of AE collection are not considered AEs. However, if a pre-planned procedure is performed early (e.g. as an emergency) due to a worsening of the pre-existing condition, the worsening of the condition will be captured as an AE. Elective procedures planned or performed where there is no change in the subject's medical condition will not be recorded as AEs, but will be documented in the subject's source documents.

### **12.5.4 Overdose Reporting**

Cases of study drug overdose without manifested side effects are NOT considered AEs.

### **12.5.5 Clinical Laboratory Abnormalities and Other Abnormal Assessments**

All laboratory values must be reviewed by the Investigator or medically qualified designee as soon as practical after the data are available.

Any laboratory values outside the reference range will be evaluated for clinical significance. Laboratory abnormalities that occur without related clinical symptoms and signs should generally not be recorded as AE unless they represent a clinically significant event. Where possible, the overall diagnosis rather than the laboratory abnormality should be recorded on the AE CRF. This will avoid duplication of laboratory abnormalities in both the AE and laboratory reports. Abnormal laboratory results that are of clinical significance should be reviewed by the Medical Monitor.

Any laboratory test result that meets the criteria for a SAE (refer to [Section 12.3](#)) should be recorded as an AE, the AE page of the CRF completed and a SAE form also completed in order for the

sponsor to collect additional information about that abnormality, including information regarding relationship to study product or other causes, any action taken and resolution.

## **12.6 Guidance for Dose Modification or Discontinuation of Treatment**

Dose modification or discontinuation of treatment are not applicable in this single dose study.

## **12.7 Warnings and Precautions**

For information regarding precautions and AEs with the investigational drug, the Investigator is referred to the Investigator's Brochure and Prescribing Information for moxidectin.

## **12.8 Risks for Women of Childbearing Potential or During Pregnancy**

The risks of treatment with moxidectin during pregnancy have not been evaluated. Women of child-bearing potential must agree not to attempt to become pregnant. If participating in sexual activity that could lead to pregnancy, women of child-bearing potential and male partners of women of child-bearing potential must agree to use a reliable method of contraception during the study and for the 6 months following study drug administration.

## **12.9 Procedures to be Followed in the Event of Pregnancy**

The subject must be instructed to inform the Investigator **immediately** if she becomes pregnant during the study period or if his partner becomes pregnant. The Investigator should report all pregnancies to the Sponsor or designee within 24 hours of becoming aware of the pregnancy. Pregnancies should be reported using Clinical Pregnancy Notification Form provided by the Sponsor for reporting the occurrence and outcome of pregnancies in subject enrolled in the study.

The subject should be monitored until the end of the pregnancy and the outcome of the pregnancy should be reported to the Sponsor.

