#### 5.3.2.1 Clinical Pharmacology

Moxidectin displays linear, dose-proportional pharmacokinetics. Following a single oral moxidectin dose (ranging from 3 mg to 36 mg, tablet or solution) administered to fasting healthy volunteers, the non-compartmentally-derived apparent moxidectin plasma clearance (CL/F) ranged from 1785 to 3506 mL/h and the mean  $t_{1/2}$  ranged from 485 to 1139 hours (approximately 20 to 47 days).

Moxidectin was rapidly absorbed; the median time of maximum observed plasma concentration ( $t_{max}$ ) in a fasted state was 3 to 4 hours post-dose. Moxidectin has a large apparent volume of distribution, and rapid decline of moxidectin concentrations occurred within 48 hours of dose administration in all studies, and, thereafter, plasma concentrations declined slowly in accordance with the long  $t_{1/2}$ . Population pharmacokinetic analyses showed that the long  $t_{1/2}$  was governed by tissue distribution rate-limited elimination.

There was no clinically relevant effects of age, gender, race, weight, renal function or hepatic function on the pharmacokinetics of moxidectin from a population-pharmacokinetic model. Moxidectin absorption is resilient to the effects of food. Administration of moxidectin in a fed state modestly slows absorption and increases bioavailability, although not to a clinically relevant extent. Moxidectin does not induce or inhibit clinically relevant drug-drug interactions and it is unlikely to be a victim of drug-drug interactions via concomitant medications.

Moxidectin is minimally metabolized and primarily excreted unchanged in the feces. Renal clearance of moxidectin and its metabolites is low. Moxidectin was observed in the breast milk of lactating women after single dose administration at a relative infant dose of less than 10% of the maternal dose.

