### 7.4 Estimated Duration of the Study

The study is expected to take approximately 18 months to complete. The on-study period per subject is 13 weeks, consisting of one week for Screening and 12 weeks post-treatment.

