### 8.2 Inclusion Criteria

A subject must meet all of the following inclusion criteria:

1. Aged  $\geq 18$  years.
2. Provision of written informed consent.
3. Parasitologically confirmed active *Sarcoptes scabiei* infestation, defined as the presence of at least two lesions (which may include burrows), each containing at least one live (internal and/or external structures discernable) adult *Sarcoptes scabiei* mite observed by RCM.
4. Agree to the use of reliable contraceptive measures if female or male partner of a female of child-bearing potential from Screening until 6 months after treatment with study drug ([Section 8.4.2](#)).

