### 8.4.2 Contraception

All women of child-bearing potential (defined as sexually mature women who have had menses within the preceding 24 months and have not undergone hysterectomy, bilateral oophorectomy or tubal ligation) must have a negative pregnancy test at Screening. Pregnancy testing may be performed by analysis of serum or urine and should be confirmed at Baseline prior to study drug administration. Pregnancy testing will be repeated at Week 12.

Women of child-bearing potential must agree not to attempt to become pregnant. If participating in sexual activity that could lead to pregnancy, women of child-bearing potential and male partners of women of child-bearing potential must agree to use a reliable method of contraception during the study and for the 6 months following study drug administration.

Women who are not of reproductive potential (who have been postmenopausal for at least 24 consecutive months or have undergone hysterectomy, bilateral oophorectomy or tubal ligation) are not required to use contraception.

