### 9.2 Visit Windows

Screening must be conducted after informed consent has been given, in the window of Day -7 to Day -1.

All visit days are calculated from Day 0, which is the date of the Baseline (pre-dose) assessments and study drug administration. Hours are calculated based on the time of administration of moxidectin.

Windows for each study assessment are:

- $\pm$  15 minutes for Hours 2 and 3,
- $\pm$  30 minutes for Hour 4,
- $\pm$  1 hour for Hour 8,
- $\pm$  4 hours for Hours 24, 48 and 72,
- $\pm$  2 days for Days 7 and 14,
- $\pm$  3 days for Day 28,
- $\pm$  7 days for Week 12.

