### 9.3.4 Study Conclusion (Week 12)

At Week 12, the subject will return to the clinic for the following assessments:

- Adverse event assessment (see [Section 12](#)).
- Recording of concurrent medications (see [Section 11](#)).
- A modified physical examination including body weight (see [Section 9.4.3](#)).
- Vital signs assessment (see [Section 9.4.4](#)).
- For women of childbearing potential, confirmation of a negative pregnancy test (see [Section 9.4.6.2](#)).

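### Section 12.9 asks female subjects to report a pregnancy only during an undefined study period, most naturally ending at Week 12, although contraception is required for 6 months after dosing

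*Protocol*

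**What the plan says.** - **Reporting by the subject (Protocol 12.9).** She must be told to inform the Investigator immediately "if she becomes pregnant during the study period or if his partner becomes pregnant". The clause about a male subject's partner has no end date.
- **Reporting by the Investigator (Protocol 12.9).** Every pregnancy goes to the Sponsor within 24 hours of the Investigator learning of it, with no end date, and is followed to its outcome.
- **Length of study for one subject.** Protocol 7.4: "The on-study period per subject is 13 weeks, consisting of one week for Screening and 12 weeks post-treatment". Section 9.3.4 names the Week 12 visit as the conclusion of the study, and Section 15.5.2 ends Period 2 at Week 12. SAP Sections 2.3 and 5.2 agree.
- **Contraception.** Inclusion criterion 4 (Protocol 8.2) applies "from Screening until 6 months after treatment with study drug". Section 12.8 says that those concerned "must agree to use a reliable method of contraception during the study and for the 6 months following study drug administration", and Section 8.4.2 has the same requirement.
- **Last test.** Protocol 8.4.2: "Pregnancy testing will be repeated at Week 12". No later visit, test or contact is scheduled.

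**The concern.** The sponsor asks women to avoid pregnancy for 6 months, but the instruction to report one appears to stop at about 3 months. Section 12.8 states that the risks of moxidectin in pregnancy have not been evaluated, and Section 12.9 wants pregnancies reported and followed to outcome. The drug is eliminated slowly, so a conception soon after Week 12 may still be exposed. Once visits have ended, the site would normally learn of such a pregnancy only from the subject, and the instruction to her is the one that is time-limited. What is at stake is the completeness of safety information on a small number of possible exposures.

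**Working it through.** **1. The plan's own duration.** Screening is up to 7 days and follow-up is 12 weeks: 7 + 12 × 7 = 91 days = 13 weeks. This matches the 91 days in the synopsis and the 13 weeks in Section 7.4.

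**2. Length of the gap.** Inputs, counted from the dose on Day 0:
- end of study for one subject: Week 12 = Day 84, with a window of plus or minus "7 days for Week 12" (Section 9.2), so Day 77 to Day 91;
- end of contraception: 6 months, taken as 26 weeks = 182 days (assumption).

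Gap = end of contraception − end of study:
- nominal: 182 − 84 = 98 days = 14 weeks, and 98/182 = 54% of the period;
- late visit: 182 − 91 = 91 days = 13 weeks;
- early visit: 182 − 77 = 105 days = 15 weeks.

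Taking 6 months as 180 to 184 days moves the nominal gap to between 96/7 = 13.7 and 100/7 = 14.3 weeks. With the visit window as well, the extremes are (180 − 91)/7 = 12.7 and (184 − 77)/7 = 15.3 weeks.

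**3. Drug remaining in the gap.** Section 5.3.2.1 reports a rapid fall within 48 hours and a slow decline afterwards, with mean half-lives of 485 to 1139 hours, that is 485/24 = 20.21 days to 1139/24 = 47.46 days. Assuming single-exponential decline from 48 hours (Day 2), the share of the 48-hour concentration left on Day d is 2^(−(d − 2)/half-life).

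| Day | Half-life 20.21 d | Half-life 47.46 d |
|---|---|---|
| 77 | 2^(−75/20.21) = 7.6% | 2^(−75/47.46) = 33.4% |
| 84 | 2^(−82/20.21) = 6.0% | 2^(−82/47.46) = 30.2% |
| 91 | 2^(−89/20.21) = 4.7% | 2^(−89/47.46) = 27.3% |
| 182 | 2^(−180/20.21) = 0.2% | 2^(−180/47.46) = 7.2% |

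The synopsis gives an upper half-life of 43 days instead. The upper values then become 2^(−82/43) = 27% at Day 84 and 2^(−180/43) = 5.5% at Day 182, which does not change the picture.

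**4. Is the gap closed elsewhere?** Three other provisions come near it:
- the Investigator's duty in Section 12.9 starts only when the Investigator becomes aware;
- Section 12.2.2 makes possibly related adverse events reportable at any time, but does not name pregnancy;
- Section 12.3.1 makes a congenital anomaly in a subject's child a serious event.

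Each works only once the site knows. A late pregnancy with a normal outcome would trigger neither of the last two.

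**The case against.** The strongest objection is that Section 12.9 directs the site to instruct the subject, and the text she actually reads is the model consent form in Appendix 18.2. That form was not in the text reviewed, and neither was the Study Reference Manual. Either may already extend the instruction to 6 months. This stands as a limit: the point concerns the wording of Section 12.9 and cannot show that subjects were left uninformed.

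Second, the study period could mean the whole trial, about 18 months in Section 7.4, which would shrink or remove the gap for women enrolled early. That reading is weaker, because the per-subject definitions all end at Week 12 and Section 12.8 words the study and the 6 months as separate spans. It would also make coverage depend on enrollment date and leave the last woman dosed with no instruction after her final visit.

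Third, the residual percentages show that drug persists, not that it does harm. They are relative to the 48-hour level, so the share of the peak is lower still. The documents give no plasma threshold for fetal harm. Section 5.3.1.3 reports malformations in rats at maternally toxic doses but not in rabbits, no genotoxicity, and reduced survival of rat pups during lactation. This is fair, and no risk is inferred from the percentages.

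Fourth, very few events are likely. At most about 36 adults of both sexes are planned, and those who could conceive must agree to contraception. This stands too, and is why the point is minor.

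**Conclusion.** The concern holds as a minor gap in safety capture. Read with Sections 7.4, 9.3.4 and 15.5.2, Section 12.9 gives a female subject no instruction to report a pregnancy that begins in about the last 14 of the 26 weeks for which contraception is required (13 to 15 weeks with the visit window). This rests on two assumptions: that the undefined study period ends at Week 12, and that 6 months is 26 weeks. About 6% to 30% of the 48-hour plasma level would remain when the gap opens and 0.2% to 7% when it closes, assuming single-exponential decline at the mean half-lives in Section 5.3.2.1. The documents give neither the number of women of child-bearing potential nor a pregnancy rate, so no event count can be offered. Confidence is medium because the consent form was not seen. The open-ended partner clause is not at fault, and no efficacy endpoint, analysis or dose decision changes.

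**What to change.** In Section 12.9, replace the time limit in the female clause with: at any time from Screening until at least 6 months after dosing. The sponsor can drop the words *at least* if it prefers a fixed end date. Leave the partner clause exactly as it is, so that nothing is narrowed. Add one line to Section 9.3.4 so that the instruction is repeated at the Week 12 visit, and check that Appendix 18.2 says the same.

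The cost is one clause, one line and a consistency check, carried in the next amendment and submitted to the ethics committee under Sections 16.1.3 and 16.1.4. No visit, test or form is added. The site may receive an occasional report after the last visit, which the existing pregnancy notification form can handle, with follow-up to outcome. Late capture would still depend on the subject making contact, but she would have been told to.
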